11.2 Standard Intervention Group

The standard intervention components are described in Exhibit 2. Staff Coaches and Peer Leaders will participate in all trainings.

Exhibit 2. Overview of Standard Intervention Components		
	Component	Elements
Standard	On-Board Training	During training sessions, a mix of didactic content and role play are used. Materials needed to implement all components the ACHIEVE weight-loss curriculum is covered. More detail on how to discuss each weight-loss subject is introduced in a stepwise fashion. Training on motivational interviewing (MI) techniques is also provided. Master trainers who have expertise in health coaching and MI training conduct the initial on-board training.
	Online Training Modules	Monthly online didactic training modules (15-20 min) are an efficient method for coaches to observe and learn how to deliver the ACHIEVE weight-loss topics. Each training module includes both relevant didactic content and examples of experienced ACHIEVE staff providing real-world examples of delivering the content in groups. Coaches view the online modules each month before teaching that specific component of the program.
	Online Avatar MI Practice Module	At the end of the on-board training, coaches are given access to an online avatar MI practice module, which includes a 15-minute didactic component and 15-minute virtual practice conversations with consumers with SMI. These simulated conversations allow coaches to practice (a) providing feedback about weight-loss progress and (b) increasing participant engagement in exercise classes. The avatar module includes built-in MI performance feedback. Coaches are encouraged to use the module weekly for the first three months and as needed (e.g., monthly), repeating practice until they receive a "good" score.

Our training approach provides interactive opportunities for coaches to practice the skills needed to implement the ACHIEVE curriculum, a strategy more effective than didactic education.

At minimum, each Coach will be video-recorded delivering an ACHIEVE group during months 1, 3 and 6; each coach may be recorded monthly. These recordings will be for research purposes only and will not be shared with the site supervisors. Recordings will be shared with master trainers on the study team who are responsible for assessing fidelity to the ACHIEVE curriculum (master trainer grading will not be used in outcome scoring).

To enhance the uptake of ACHIEVE we will meet with leadership for organizational strategy meetings to increase leaders' engagement with evidence-based practice implementation. These meeting will be held approximately monthly and will include the PRP director and ACHIEVE coaches. These meetings support development, adoption, and sustainment of organizational strategies needed for program implementation (e.g., changes to class schedules to maximize attendance) as well as implement strategies that demonstrate leadership buy-in to ACHIEVE.

11.3 Enhanced Intervention Group

The enhanced intervention includes all components of the standard intervention along with the addition of performance coaching. Performance coaching may be particularly beneficial when, as in the present case, the evidence-based practice is new to most implementers. Each month a master trainer on the study team will meet with the Coach to provide tailored feedback and performance coaching session. The feedback will be used to 1) promote curriculum fidelity; 2) facilitate motivational interviewing skill development; and 3) help coaches plan for improved ACHIEVE curriculum delivery.

12. DATA MANAGEMENT and SECURITY

Quantitative Data. Each participant will be assigned a unique study ID number for data collection, instead of name or other identifying information. The link between identifying information and the study ID will be kept in a separate database with password access available only to the data analyst, statistician and principal investigators. Study team members are trained to protect integrity and confidentiality of the data. Data will be published only in aggregate, with no identifying characteristics of individuals published or presented. We will store data in a Johns Hopkins REDCap database. REDCap data is housed on secure servers at the Johns Hopkins Biostatistics Center under firewall protection. Database access is password protected and restricted to authorized personnel only and REDCap provides audit trails for tracking data manipulation and user activity. Any paper records will be kept in locked file cabinets. Kognito, a health simulation company, developed the avatar simulations for this project and hosts the avatar training platform and dashboard. Avatar performance measurement data for motivational interviewing practice conversations is accessible only by the individual study participant (provider) and the study team, not shared outside Kognito. Kognito stores data securely behind two firewalls.

Built-in range and logic checks will prompt data checks and confirmation in real-time during data collection. The analyst will routinely conduct thorough checking and cleaning, examining distributions and data patterns and evaluation to detect inconsistencies. Outliers (e.g., extreme weight changes) will be identified using Rosner's extreme Studentized deviate (ESD). Every effort will be made to determine correctness of outliers in a timely manner. Confirmed outliers will be flagged and set aside in the principal secondary analyses. Those removed will be treated as all other missing data; sensitivity analyses will be conducted to assess influence of outliers on results. The analyst will create detailed variable documentation and conduct analysis per protocol under direction of [name], statistician.

Qualitative Data. Focus groups will be audio or video-recorded and recordings will be transcribed using Production Transcripts, Inc or another approved Johns Hopkins vendor. Names will be removed from transcripts. Recordings will be stored in a Johns Hopkins secure network drive and will be destroyed when analyses are complete. Standardized actor interview recordings will be reviewed by experts in motivational interviewing for fidelity to motivational interviewing practices and stored in a Johns Hopkins secure network drive or OneDrive.

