A successful behavioral weight-loss intervention tested in an RCT within the SMI population

The NIMH-funded ACHIEVE trial was the first to demonstrate that an adapted behavioral intervention leads to clinically significant weight loss at 18 months among persons with SMI (mean 7 lbs. weight loss, net 3% loss)¹⁵. The magnitude of weight loss among individuals with SMI participating in ACHIEVE was similar to the

magnitude observed in efficacious weight-loss trials in general populations¹¹. The ACHIEVE intervention combined group and individual weight-management sessions with group exercise sessions delivered in community mental health programs^{14,15}. To address some of the noted challenges in this population^{12,13}, the intervention focused on repeated delivery of six key messages: avoid sugary drinks, avoid junk food, eat 5 servings of fruits/vegetables per day, portion control, smart snack habits, and regular physical activity. The ACHIEVE intervention was predominantly delivered by trained study interventionists, though mental health program staff delivered some video-assisted group exercise sessions^{14,15}. Given the obesity epidemic in persons with SMI, there is an urgent need to “scale-up” or expand ACHIEVE to similar settings and populations as those included in the RCT, which we posited could be accomplished by enabling the psychiatric rehabilitation program staff to deliver the sessions¹⁶. Using the Enhanced Replicating Effective Programs Framework for translating evidence-based interventions into community settings¹⁷, our scale-up strategy considers this model’s three stages: pre-implementation, implementation, and dissemination.

Scaling up ACHIEVE – pre-implementation stage

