
 • Any underlying medical conditions that could seriously reduce life expectancy, ability to participate in the study, or for which dietary change/physical activity/weight loss may be contraindicated e.g., 
 ◦ Lung disease requiring supplemental oxygen ◦ Liver failure ◦ History of anorexia nervosa or bulimia ◦ Stage V kidney disease on dialysis ◦ Cardiovascular event in the last 6 months including unstable angina, myocardial infarction, congestive heart failure, transient ischemic attack, or stroke • Insulin dependent diabetes • Inability to walk unassisted (e.g., uses a cane, walker, etc) • Pregnant, breastfeeding, or planning a pregnancy during study period • Prior or planned bariatric surgery • Use of a prescription anti-obesity medication or over-the-counter orlistat within the past 3 months • Self-reported weight loss of $>20 \text{ lbs}$ in the last 3 months • Active substance use disorder, alcohol use disorder, or problem drinking (more than 14 drinks per week for women, more than 21 drinks per week for men) • Planning to leave mental health program or move out of geographic area within 12 months • Weight greater than 440 pounds (so as not to exceed capacity of study scale) • Investigator judgment (e.g., for concerns over safety, adherence or follow-up)

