13. DATA ANALYSIS

We will assess the effects of the implementation intervention on providers' knowledge self-efficacy, and fidelity to the ACHIEVE curriculum, as well as consumer outcomes using generalized linear mixed-effects models under the intent-to-treat approach. Mean models will include a binary intervention group indicator, time indicators, intervention by time interaction terms, and fixed effects for the 10 study sites. The time indicator coefficients estimate time-specific mean outcome changes in the "standard" group and interaction coefficients estimate the between-arm differences of time-specific outcome changes from baseline. The linear combination of these time-specific coefficients captures the time-specific mean outcome changes in the "enhanced" group. The model will use an unstructured variance covariance matrix for the repeated outcome measurements over time within individuals. To assess whether knowledge and self-efficacy mediate implementation intervention

effects, we will estimate the magnitude of attenuation on intervention effects in the consumer outcome models with vs. without these measures. We will also examine potential moderators, e.g. study sites' implementation intervention fidelity and/or implementation climate, by adding appropriate interaction terms to the models. We will analyze survey data on our implementation measures prior to conducting focus groups in order to explore survey findings in depth (e.g., if providers' rate performance coaching as having mediocre acceptability, we will explore reasons why in the focus groups). We will use descriptive statistics to analyze survey measures of perceptions of acceptability, feasibility and appropriateness of implementation intervention and ACHIEVE-D. Point estimates and corresponding 95% confidence intervals will be obtained.

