Nutrient intake: Calorie restriction could theoretically lead to inadequate nutrition or excessive, rapid weight loss. Intervention subjects will be encouraged to eat a variety of foods from all food groups and maintain an adequate caloric level. Those who have a sudden, marked weight reduction will be interviewed to determine if extreme measures have been taken. The issue of adequate nutrient intake and the importance of safe weight loss will be discussed in the group and individual sessions. If a problem is suspected, the participant will be counseled.

Hypoglycemia related to diet and exercise interventions: For patients who may be susceptible to hypoglycemia due to use of anti-diabetic medications, weight loss interventions have the potential to increase the risk of hypoglycemia, especially during the time when diet and/or physical activity interventions are implemented. To minimize the risk of hypoglycemia, we will require primary care physician approval prior to enrolling individuals with diabetes.

Symptomatic hypotension related to diet and exercise interventions: For patients who may be susceptible to hypotension because they are using medications that lower blood pressure, weight loss interventions have the potential to increase the risk of hypotension. Participants are educated about symptoms of hypotension and urged to contact their primary physician if they have symptoms suggestive of hypotension. In addition, staff will notify primary physicians for participants who develop symptomatic hypotension while on anti-hypertensive medications.

Alert Values for baseline blood pressure data collection

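### The outlier rule in Section 12 appears to drop verified true values, such as large weight losses, from the main secondary analysis

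*Combined protocol and SAP*

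**What the plan says.** Section 12 (Data Management and Security) sets out four steps.

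1. Outliers are identified by Rosner's extreme Studentized deviate (ESD), a test based only on size. Large weight changes are the example given.
2. The values are checked: "Every effort will be made to determine correctness of outliers in a timely manner".
3. "Confirmed outliers will be flagged and set aside in the principal secondary analyses".
4. "Those removed will be treated as all other missing data; sensitivity analyses will be conducted to assess influence of outliers on results".

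The section names no study population. It gives no significance level for the ESD test, no maximum number of outliers, and no statement on whether arms are pooled. *Confirmed* is not defined, and the term *principal secondary* analyses appears nowhere else.

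Section 13 (Data Analysis) plans to analyse "consumer outcomes using generalized linear mixed-effects models under the intent-to-treat approach" and mentions no outlier exclusion. Its model reports change within arm as well as between arms: "The time indicator coefficients estimate time-specific mean outcome changes in the" standard arm, and the arm-by-time terms give the difference. Consumer weight is one of the outcomes in Secondary Aim 2 (Section 2).

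**The concern.** Because step 3 follows a check of correctness, *confirmed* most naturally means verified as real. True observations would then leave the main secondary result because they are extreme. They would be missing not at random, since the reason for missingness is the value itself. A likelihood-based mixed model relies on missingness being explained by the observed data, so it does not repair this. Removal by size also sits badly with the intent-to-treat approach of Section 13.

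Weight is the likely outcome affected, by inference from the plan's own example. The protocol allows for true large losses. Section 16 says: "Those who have a sudden, marked weight reduction will be interviewed to determine if extreme measures have been taken". The exclusions in Table 3 of Section 7.1, such as "Prior or planned bariatric surgery", make such values rarer but do not rule them out. Large losses also lie in the direction that the curriculum aims for (5% in 6 months, Section 11.1, Exhibit 1).

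At stake is the estimated weight change within each arm and, if true extremes fall unequally, the difference between arms.

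**Working it through.** **The wording.** The plan gives no figure to reproduce, so the first check is of the text. If *confirmed* meant confirmed as an error, step 4 would be studying the influence of values already known to be wrong, which has little purpose. The influence of real values is worth studying. Step 4 therefore favours the reading verified as real, without settling it.

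**Inputs.** From the plan: at most 120 consumers (Section 4), so 60 per arm; 10 sites; the Section 13 model. Assumed, because the plan gives none: mean change −3 lb; SD of change 8, 10 or 12 lb; intraclass correlation of change by site 0.05; baseline mean 220 lb and SD 45 lb; true losses of about 40 lb; ESD with arms pooled, alpha 0.05 and at most 8 outliers.

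**When a single value is flagged.** The first ESD critical value is λ = (n−1)t / √[(n−2+t²)n], where t is the 1−0.05/(2n) quantile of the t distribution on n−2 degrees of freedom. For n = 120, λ = 3.445. The outlier itself inflates the SD, so it must lie at distance d from the mean of the other values:

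d = σ · λ√[(n−2)/(n−1)] / √{[(n−1)/n]² − λ²/n} = σ · 3.4305/0.9405 = 3.648σ

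Adding the mean loss of 3 lb gives thresholds of 32.2, 39.5 and 46.8 lb at SD 8, 10 and 12.

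**Hand calculation.** A 40-lb loss lies 37 lb from the mean. Removing one from an arm of 60 shifts that arm's mean by 37/60 = 0.62 lb. Removing three shifts it by 3 × 37/60 = 1.85 lb.

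**Section 13 model refitted.** Baseline and 6-month weight, site fixed effects, time, arm-by-time and an unstructured covariance were fitted by maximum likelihood; the arm main effect is absorbed by the site effects. ESD was run on the change. Flagged 6-month values were set to missing and the baseline kept. There were 600 data sets per cell, and the Monte Carlo error of the shift was 0.04 lb or less. Arm difference in lb (enhanced minus standard), full data → after removal:

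| 40-lb losses, enhanced:standard | SD 8 | SD 10 | SD 12 |
|---|---|---|---|
| 1:0 | −0.64 → −0.03 | −0.67 → −0.29 | −0.78 → −0.71 |
| 2:1 | −0.55 → 0.06 | −0.52 → −0.25 | −0.59 → −0.59 |
| 3:0 | −1.76 → 0.08 | −1.94 → −1.09 | −1.91 → −1.87 |
| 3:3 | 0.08 → 0.08 | −0.08 → −0.09 | 0.02 → 0.02 |

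In the 3:0 case the mean number of values removed was 3.03, 1.35 and 0.07. A simple difference in means (2,000 data sets per cell) shifted by 1.82, 0.80 and 0.03 lb for 3:0 and by 0.61, 0.28 and 0.01 lb for 2:1. The mixed model shifts by about the same amount, so keeping the baseline does not undo the removal.

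**Against the standard error.** With three losses and full data, the model SE is 1.77, 2.06 and 2.38 lb. The worst case is 1.84/1.77, about one SE. A 2:1 split at SD 8 is 0.61/1.77, about a third of an SE. After removal the SE is 1.46, 1.93 and 2.37 lb, so precision is overstated at SD 8.

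**Overall mean change.** Three losses in all: −3.9 → −3.0, −4.0 → −3.6, no change. Three per arm: −4.8 → −3.0, −4.9 → −4.4, no change. For scale, the earlier trial reported "mean 7 lbs. weight loss, net 3% loss" at 18 months (Section 3).

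**Smaller trial.** At 8 consumers per site there are 5 × 8 = 40 per arm. Without site correlation, the shifts are 0.90, 0.43 and 0.03 lb (2:1) and 2.72, 1.31 and 0.11 lb (3:0). The largest is 2.72/2.35, about 1.2 SE.

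**Where little happens.** With normal tails about 0.05 values are removed per trial. Three 30-lb losses in one arm shift the difference by 0.21 lb at SD 8 and by nothing at SD 10 or 12.

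**The case against.** The strongest reply is that this is a wording query. The sentence stands in the data-management section, at the end of a cleaning sequence, where confirmed as an error fits. Section 13 places consumer outcomes under intent-to-treat without mentioning exclusions, so the set-aside may belong to an analysis beside the main one. If either term resolves that way, no bias remains. That is fair, and it is why the plan must say which is meant. It does not remove the point: a rule on which values enter a main result should not permit opposite readings, and the plan to assess influence favours the adverse one.

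Second, sensitivity analyses are already promised, so both results would exist. This limits the harm, but the truncated estimate would still be the principal one.

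Third, the size rests on assumed data. No document gives an SD or a frequency of 40-lb losses, and both arms receive the same consumer curriculum, so nothing supports a 3:0 split. This stands; the figures are illustrative. It also stands that only losses were simulated, while ESD is two-sided and Section 3 notes that the medications promote weight gain. With two 40-lb losses and two 34-lb gains at SD 8, the overall mean was −3.01 lb before and after removal. True gains can therefore cancel the shift in the mean, but they do not make it sound to delete verified values.

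Fourth, keeping values that cannot be resolved is partly a matter of preference. That is correct, and the main remedy does not depend on it.

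**Conclusion.** The concern holds. On the natural reading of Section 12, values verified as true are removed from the main analysis of a secondary outcome because of their size. This should be corrected, but the consequence is modest. Under the assumed inputs with 60 per arm, the arm difference moves by nothing to about one SE (1.8 lb), depending on the SD and on how unequally true extremes fall. If the extremes are in the enhanced arm, the shift is toward zero; if in the standard arm, it is the other way. With equal numbers in each arm the difference is unchanged, but the within-arm change and the SE can still be distorted. Confidence is medium, because two undefined terms could resolve benignly and because weight is inferred from the plan's example. The coach-level primary outcomes of knowledge, self-efficacy and fidelity are not affected.

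**What to change.** In Section 12:

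- State that only values shown to be measurement or entry errors are corrected or set to missing.
- State that values verified as correct stay in the main analysis of the secondary outcomes. For values that cannot be resolved, state a rule in advance; keeping them is the suggested default.
- Make exclusion of ESD-flagged values, or a robust analysis, the sensitivity analysis. Give its alpha, the maximum number of outliers, and whether it is run pooled and blind to arm.
- Use the class weigh-ins already collected (Sections 7.3 and 11.1) to help verify an extreme 6-month weight, since Section 7.3 allows self-measured weight.

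If *confirmed* was meant as confirmed to be an error, saying so in that sentence is enough.

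The core change needs one or two sentences and no new data. It has two costs. The variance is larger when true extremes are kept: the model SE is 1.77 instead of 1.46 lb with three losses at SD 8, and 2.38 instead of 2.37 lb at SD 12. There is also some risk of keeping an undetected error: one false 40-lb loss in an arm of 60 would shift the difference by 37/60 = 0.62 lb, which the sensitivity analysis would show.

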13. DATA ANALYSIS

We will assess the effects of the implementation intervention on providers' knowledge self-efficacy, and fidelity to the ACHIEVE curriculum, as well as consumer outcomes using generalized linear mixed-effects models under the intent-to-treat approach. Mean models will include a binary intervention group indicator, time indicators, intervention by time interaction terms, and fixed effects for the 10 study sites. The time indicator coefficients estimate time-specific mean outcome changes in the "standard" group and interaction coefficients estimate the between-arm differences of time-specific outcome changes from baseline. The linear combination of these time-specific coefficients captures the time-specific mean outcome changes in the "enhanced" group. The model will use an unstructured variance covariance matrix for the repeated outcome measurements over time within individuals. To assess whether knowledge and self-efficacy mediate implementation intervention

effects, we will estimate the magnitude of attenuation on intervention effects in the consumer outcome models with vs. without these measures. We will also examine potential moderators, e.g. study sites' implementation intervention fidelity and/or implementation climate, by adding appropriate interaction terms to the models. We will analyze survey data on our implementation measures prior to conducting focus groups in order to explore survey findings in depth (e.g., if providers' rate performance coaching as having mediocre acceptability, we will explore reasons why in the focus groups). We will use descriptive statistics to analyze survey measures of perceptions of acceptability, feasibility and appropriateness of implementation intervention and ACHIEVE-D. Point estimates and corresponding 95% confidence intervals will be obtained.

